## Part B:

No primary efficacy endpoint is defined for Part B of the study. The primary objective for Part B is to evaluate the long-term safety and tolerability of GWP42003-P, evaluated by assessing the frequency of TEAEs; laboratory tests; vital signs; ECGs; Tanner Staging, and C-SSRS results. Data will be presented as per [Section 9.4.5](#).

### 9.4.2.1. Missing Data

To ensure consistency with the previous pivotal trials in DS, LGS and TSC, missing data will be imputed using methodology implemented in the previous pivotal trials. More specifically, for participants missing seizure data due to withdrawal or intercurrent events, a 28-day average is imputed for each participant as

$$\frac{\text{Number of seizures recorded in the period for participant}}{\text{Number of days that seizure data was recorded for participant in the period}} \times 28$$

The change in seizure frequency from baseline is calculated using the imputed value.

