#### **Part B:**

Participants not entering Part B or who discontinue IMP early will down-titrate over a period of 10 days. Participants eligible to enter Part B will enter the blinded transition period. Part B GWP42003-P will be titrated to 10 mg/kg/day whilst blinded IMP is simultaneously tapered down to zero. For participants who are tolerating IMP at 10 mg/kg/day and require further reduction of seizures, dose escalation up to a maximum daily dosage of 20 mg/kg/day may occur after Day 15 based on the investigator's assessment of safety and tolerability. The IMP dose may be increased by increments of 2.5 mg/kg BID (5 mg/kg/day) no more rapidly than every 7 days, up to a maximum daily dosage of 20 mg/kg/day.

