Participants will complete weekly scheduled phone visits at Day 8 (Visit 4), Day 15 (Visit 5), and Day 22 (Visit 6) and complete an in-clinic visit at Day 29 (Visit 7) and an in-clinic or home visit for review of symptoms and safety laboratory tests and to return/dispense IMP at Day 57 (Visit 8). Participants will then return to the study site for an end of treatment visit (Day 99 [Visit 9]). If a participant withdraws from the study prematurely (ie, before the end of treatment visit), an early withdrawal visit will be conducted, and a safety follow-up phone call will occur 4 weeks after their last dose of IMP. If a participant discontinues IMP prematurely, they should be encouraged to complete the end of treatment visit and the taper period and remain in the study.

Participants not continuing to Part B will return to the study site again at the end of the 10-day taper period (Day 110 [Visit 10]) and will complete a phone safety visit at the end of the follow-up period (Day 138 [Visit 11]).

Part B will be available to participants who complete Part A of the study and continue to meet all eligibility criteria and to participants for whom the investigator feels continued treatment in Part B represents a favorable risk-benefit assessment. Rollover into Part B should occur on the same day as Part A Day 99 (Visit 9).

Unscheduled phone visits can occur at any time throughout Part A, as needed.

AE, concomitant medication, and rescue medication eDiaries will be completed each day during the screening period, baseline observation period, treatment period, and taper period beginning at screening (Visit 1).

Seizure eDiaries will be completed each day during the screening period, baseline observation period, and treatment period beginning at screening (Visit 1).

IMP dosing eDiaries will be completed each day during the titration, treatment, and taper periods beginning at randomization (Visit 3).

Food eDiaries will be completed for approximately 24 hours prior to each visit where PK blood samples will be collected beginning approximately 24 hours prior to randomization (Visit 3).

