## 7.2. Participant Withdrawal from the Study

A participant may withdraw from the study at any time at his/her own request or may be withdrawn at any time at the discretion of the investigator or sponsor for safety, behavioral, or compliance reasons.

- The participant will be permanently discontinued both from the IMP and from the study at that time.
- If a participant is withdrawn from the study, the study monitor will be informed immediately. If there is a medical reason for withdrawal, the participant will be followed up by the investigator until satisfactory health has returned.
- All efforts must be made to complete and report the observations as thoroughly as possible up to the date of withdrawal.
- Participants withdrawing due to an AE should be followed up according to [Section 10.4.4](#). All information should be reported on the applicable eCRF pages (refer to [Section 8](#)). A safety follow-up visit should take place  $\pm 7$  days after last dose of IMP (refer to [Table 1](#) and [Table 2](#)). If withdrawing participants decline to give a reason for withdrawal of consent, the investigator must respect the participant's wishes.
- If the participant withdraws consent for disclosure of future information, the sponsor may retain and continue to use any data collected before such a withdrawal of consent.
- If a participant withdraws from the study, he/she may request destruction of any samples taken and not tested, and the investigator must document this in the site study records.

Reasons for removal of a participant from the study are:

- Decision by investigator.
- Decision by sponsor.
- Lack of efficacy.
- AE.
- Withdrawal by participant/caregiver/legal representative.
- Death.
- Lost to follow up.

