### **7.3. Lost to Follow up**

A participant will be considered lost to follow-up if he or she fails to return for scheduled visits and/or is unable to be contacted by the study site.

The following actions must be taken if a participant fails to return to the clinic for a required study visit:

- The site must attempt to contact the participant and reschedule the missed visit as soon as possible and counsel the participant on the importance of maintaining the assigned visit schedule and ascertain whether or not the participant wishes to and/or should continue in the study.
- Before a participant is deemed lost to follow up, the investigator or designee must make every effort to regain contact with the participant (where possible, 3 telephone calls and, if necessary, a certified letter to the participant's last known mailing address or local equivalent methods). These contact attempts should be documented in the participant's medical record.
- Should the participant continue to be unreachable, he/she will be considered to have withdrawn from the study.
- Site personnel, or an independent third party, will attempt to collect the vital status of the participant within legal and ethical boundaries for all participants randomized, including those who did not get the IMP. Public sources may be searched for vital status information. If vital status is determined as deceased, this will be documented, and the participant will not be considered lost to follow up. Sponsor personnel will not be involved in any attempts to collect vital status information.

Discontinuation of specific sites or of the study as a whole are handled as part of [Section 10.2.9](#).

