#### **9.4.2. Primary Endpoint(s)**

##### **Part A:**

The primary efficacy endpoint is EMAS-associated seizure frequency (myoclonic-atomic, atomic, tonic, clonic, or tonic clonic) over the 14-week treatment period.

The primary estimand for this study is defined by the following 3 components:

- Target population: participants with EMAS-associated seizures who have not achieved adequate control from other ASMs.
- Endpoint: change in EMAS-associated seizure frequency during the 14-week treatment period compared to baseline.
- Measure of IMP effect: change in EMAS-associated seizure frequency during the treatment period, regardless of any intercurrent events. This measure of effect follows the treatment policy strategy for handling intercurrent events.

The analysis of the primary efficacy endpoint will utilize Bayesian methodology to borrow external data from the historical pivotal studies in DS, LGS, and TSC. Active treatment groups will be pooled across doses within each indication to achieve a single estimated historical treatment effect for each indication. A Bayesian hierarchical model that dynamically determines the amount of information to be “borrowed” from the historical studies in the estimation of the treatment effect in the EMAS population will be used ([Viele 2014](#)).

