### 9.4.2.2. Sensitivity Analyses

The following sensitivity analyses will be conducted for the primary endpoint:

- Primary endpoint analysis repeated using the following imputation methods for missing eDiary data during the treatment period only:
  - Any intermittent missing data for the number of seizures arising from unreported days in the eDiary will be imputed using the worst (highest number of seizures) of the following for each participant: LOCF, NOCB, and the mean daily number of seizures during the treatment period based on nonmissing data:

$$\frac{\text{Number of seizures}}{\text{Number of reported days in the eDiary}}$$

- For participants in the active arm who withdraw from the study due to an adverse event or lack of efficacy, missing eDiary data will be imputed as the baseline rate or the average seizure frequency during the treatment period, whichever is higher.
- To test the sensitivity of the results of the primary analysis to the degree of borrowing introduced by the dynamic borrowing prior, a model similar to the primary analysis model will explore a range of degrees of fixed borrowing of the historical data. More specifically, the variance of the Bayesian hierarchical distribution specified for the treatment effects across populations ([Section 9.4.2](#)) will be fixed across a set of values specified in the ADR ranging from very low (full borrowing) to very high (no borrowing). Summaries of the estimated treatment effect within each sensitivity analysis will be provided to assess the robustness of the primary analysis results to the degree of borrowing.

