#### **Part A:**

The first key secondary estimand for this study is defined as follows:

- Target population: participants with EMAS-associated seizures who have not achieved adequate control from other ASMs.
- Endpoint: proportion of participants who achieve  $\geq 50\%$  reduction from baseline in EMAS-associated seizures over the 14-week treatment period.
- Measure of IMP effect: proportion of responders during the treatment period, regardless of any intercurrent events. This measure of effect follows a treatment policy strategy for handling intercurrent events.

The second key secondary estimand for this study is defined as follows:

- Target population: participants with EMAS-associated seizures who have not achieved adequate control from other ASMs.
- Endpoint: CGIC score at Week 14.
- Measure of IMP effect: CGIC score at Week 14, regardless of any intercurrent events. This measure of effect follows a treatment policy strategy for handling intercurrent events.

The third key secondary estimand for this study is defined as follows:

- Target population: participants with EMAS-associated seizures who have not achieved adequate control from other ASMs.
- Endpoint: change in total seizure frequency during the 14-week treatment period compared to baseline.
- Measure of IMP effect: change in total seizure frequency during the treatment period, regardless of any intercurrent events. This measure of effect follows a treatment policy strategy for handling intercurrent events.

For the first key secondary endpoint, a binary indicator for response (at least a 50% reduction from baseline in seizure frequency over the 14-week treatment period) equaling either 1 or 0, a single Bayesian hierarchical logistic regression model will be applied to the 4 populations (DS,

LGS, TSC, and EMAS). The model will take a form similar to the primary analysis model. Complete details will be provided in the ADR.

For CGIC, a Bayesian hierarchical ordinal logistic regression model will be applied to the 4 populations. This model will take a form similar to the primary analysis model and will be detailed in the ADR.

Change in total seizure frequency will be analyzed in the same way as the primary endpoint. Full details will be provided in the ADR.

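### The post-withdrawal sensitivity rule covers 2 of 7 withdrawal reasons, and no instruction secures a Week 14 CGIC from participants who stop IMP early but stay in the study

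*Combined protocol and SAP*

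**What the plan says.** **Estimands.** Section 9.4.2 defines the primary measure as change in seizure frequency "during the treatment period, regardless of any intercurrent events. This measure of effect follows the treatment policy strategy for handling intercurrent events". Section 9.4.3.1 defines the second key secondary measure as "CGIC score at Week 14, regardless of any intercurrent events".

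**Missing seizure data.** Section 9.4.2.1 states that "for participants missing seizure data due to withdrawal or intercurrent events, a 28-day average is imputed for each participant as" the recorded seizure count divided by the number of recorded days, times 28. It gives consistency with the DS, LGS and TSC trials as the reason.

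**Sensitivity analyses.** Section 9.4.2.2, repeated in the synopsis, has two imputation rules. One is for intermittent gaps. The other reads "For participants in the active arm who withdraw from the study due to an adverse event or lack of efficacy", and fills the missing days with the higher of the baseline rate and the treatment-period average. A further analysis varies the degree of borrowing, not the imputation.

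**Withdrawal reasons.** Section 7.2 lists seven: investigator decision, sponsor decision, lack of efficacy, AE, "Withdrawal by participant/caregiver/legal representative", death and loss to follow-up. Section 7.3 adds: "Should the participant continue to be unreachable, he/she will be considered to have withdrawn from the study".

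**Stopping IMP early.** Section 4.1 says of these participants that "they should be encouraged to complete the end of treatment visit and the taper period and remain in the study". Section 7.1 asks that they stay for safety and outcome data where this is safe, feasible and agreed with the sponsor. It leaves continued scheduled activities to a documented discussion, and bars them from Part B. The synopsis says: "Participants not entering Part B or who discontinue IMP early will down-titrate over a period of 10 days".

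**CGIC timing.** In Table 1 the only Part A CGIC after screening is in the Visit 9 column, which serves as both end of treatment and early withdrawal. The food-diary item in Section 8.1.4 provides for an End of Treatment Visit ahead of Visit 9 when treatment stops early.

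**The concern.** A treatment-policy estimand needs outcomes after treatment stops, or a credible test of whatever replaces them.

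The own-average rule carries a mostly on-IMP rate into the days after withdrawal. If seizures rise off IMP, the active arm looks better than its treatment-policy value. The sensitivity analysis should show how much this matters, but the coded reason decides whether a withdrawal is tested. A caregiver who leaves because of poor response, and is coded as a caregiver withdrawal, escapes the test.

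The CGIC gap is one of data collection. If the end of treatment visit moves forward with the stop, the protocol calls for no Week 14 score, and the early score is the only one available. A later analysis plan cannot recover a rating that was never taken.

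**Working it through.** The supplied text gives no discontinuation rate or planned effect, so there is no figure in the plan to reproduce. The first and third steps compare sections; the second is an illustration on assumed inputs.

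**1. Coverage of the sensitivity rule.** Section 7.2 lists 7 reasons and Section 9.4.2.2 names 2, leaving 7 − 2 = 5. Setting death aside, 4 remain: participant or caregiver withdrawal, investigator decision, sponsor decision and loss to follow-up. The rule is also limited to the active arm.

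**2. Size.** Assumptions: on-treatment rate ratio RR = 0.70, and off-IMP days at the placebo rate. Notation: d = share of the active arm that withdraws; f = fraction of the 98 days on IMP; b = baseline rate divided by placebo treatment-period rate; s = share of withdrawals for AE or lack of efficacy. The arm effect is the mean of participant log ratios.

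- Own-average rule: log RR
- Treatment policy: (1−d)·log RR + d·log(f·RR + 1−f)
- Sensitivity rule extended to all reasons: (1−d)·log RR + d·log(f·RR + (1−f)·b)
- Sensitivity rule as written: (1−d)·log RR + d·[s·log(f·RR + (1−f)·b) + (1−s)·log RR]

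Base case, d = 0.10, f = 0.5, b = 1: log 0.70 = −0.3567 and log 0.85 = −0.1625. Treatment policy is 0.9 × (−0.3567) + 0.1 × (−0.1625) = −0.3373, a ratio of 0.7137, or a 28.6% reduction.

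Percentage reductions:

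| Case | Own average | Treatment policy | As written, s = 0.25 / 0.50 / 0.75 | Extended |
|---|---|---|---|---|
| d 0.10, f 0.5, b 1 | 30.00 | 28.63 | 29.66 / 29.32 / 28.97 | 28.63 |
| d 0.20, f 0.25, b 1 | 30.00 | 25.99 | 29.02 / 28.02 / 27.01 | 25.99 |
| d 0.10, f 0.5, b 1/0.85 | 30.00 | 28.63 | 29.49 / 28.97 / 28.45 | 27.92 |
| d 0.20, f 0.25, b 1/0.85 | 30.00 | 25.99 | 28.54 / 27.05 / 25.53 | 23.98 |

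The last two rows let the placebo rate fall 15% below baseline. Over RR 0.6 to 0.8, d 0.05 to 0.20 and f 0.25 to 0.5, the own-average rule overstates the log effect by 2.7% to 18.9%.

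For one participant, assume 28 seizures per 28 days at baseline, 14 on active treatment, and withdrawal after 28 days. The own-average rule gives 14.0, a 50% reduction and so a responder. The sensitivity rule gives (14 × 28 + 28 × 70)/98 = 24.0, a 14.3% reduction, but only if the reason is AE or lack of efficacy.

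**3. CGIC.** Section 9.4.3.1 requires the Week 14 score whatever happens. Table 1 supplies one post-screening CGIC, at the end of treatment or early withdrawal visit. Section 8.1.4 allows the End of Treatment Visit to precede Visit 9 after an early stop. Section 7.1 bars early stoppers from Part B, so no later CGIC exists. No sentence asks for a separate Week 14 rating. If 10% of the active arm stopped early and stayed, that is 3 of 30 participants (the 60-participant interim) or 6 of 60 (the maximum).

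**The case against.** - **Estimand.** A reader might infer that the missing-data rule contradicts the treatment-policy estimand. The documents do not support that. Recorded off-IMP days enter the rate, the primary rule has a stated reason, and a narrow sensitivity analysis is an incomplete check and not a contradiction.
- **Diary.** A reader might also infer that the seizure diary stops when IMP stops. Sections 4.1, 8.1.4 and 8.1.5 together carry a daily diary on for those who remain, and Section 7.1 asks for outcome data. What is left is one ambiguity: whether the end-of-taper limit in Section 8.1.4, labelled Visit 10 (Day 110), applies when the taper is early.
- **Counting reasons.** Two of seven counts categories, not participants, and the two covered are those most directly tied to drug failure. That stands, and limits how much the count alone shows.
- **The wider rule.** Applied to every reason, it would impute seizures after death. It also equals treatment policy only when baseline and placebo rates agree. With a 15% placebo fall it overshoots, and the rule as written is closer at s = 0.50 and 0.75; only at s = 0.25 is the wider rule slightly closer. This stands: the wider rule is a bound, not a better estimate.
- **Unseen documents.** Section 9.4 is a summary, and the SAP and ADR are not in the supplied text. They may add missing-data analyses. They cannot add a CGIC that the protocol does not collect.

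**Conclusion.** Both gaps hold, at modest size. The stated post-withdrawal stress test omits four non-death reasons for active-arm withdrawal, so no analysis in the protocol text varies the assumption for those participants. Following the schedule as written can also leave a key secondary estimand without its Week 14 value.

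In the base case the primary rule reports 30.0% against 28.6% under treatment policy. The sensitivity rule with half of withdrawals covered gives 29.3%, so it misses by about 0.7 percentage points. The gap of 30.0% against 26.0% needs 20% of the active arm to withdraw a quarter of the way through. All of this rests on an assumed rate ratio, withdrawal share and timing, and a full return to the placebo rate off IMP. It leaves out the borrowing model. The count of reasons and the missing CGIC instruction need no such assumptions.

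**What to change.** **(a) Section 9.4.2.2, with the synopsis to match.** Keep the own-average rule as primary and leave the historical data as they are. Add one supplementary run applying the existing higher-of-baseline-or-treatment-average rule to all active-arm study withdrawals other than death. Describe it as a conservative bound that can overshoot the treatment-policy value if placebo rates fall below baseline. A placebo-based imputation of EMAS post-withdrawal days would serve instead.

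**(b) Sections 4.1 and 8.1.4 and Table 1.** State that participants who stop IMP early but remain in the study have CGIC at Week 14 (Day 99) and continue the daily seizure eDiary to Day 99. State that a CGIC taken at an earlier visit is not analysed as the Week 14 score.

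**Cost.** A few sentences, one extra model run, and one CGIC plus a few more weeks of an existing diary for a minority of participants. The added sensitivity result may be slightly less favourable.

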### 9.4.2.2. Sensitivity Analyses

The following sensitivity analyses will be conducted for the primary endpoint:

- Primary endpoint analysis repeated using the following imputation methods for missing eDiary data during the treatment period only:
  - Any intermittent missing data for the number of seizures arising from unreported days in the eDiary will be imputed using the worst (highest number of seizures) of the following for each participant: LOCF, NOCB, and the mean daily number of seizures during the treatment period based on nonmissing data:

$$\frac{\text{Number of seizures}}{\text{Number of reported days in the eDiary}}$$

- For participants in the active arm who withdraw from the study due to an adverse event or lack of efficacy, missing eDiary data will be imputed as the baseline rate or the average seizure frequency during the treatment period, whichever is higher.
- To test the sensitivity of the results of the primary analysis to the degree of borrowing introduced by the dynamic borrowing prior, a model similar to the primary analysis model will explore a range of degrees of fixed borrowing of the historical data. More specifically, the variance of the Bayesian hierarchical distribution specified for the treatment effects across populations ([Section 9.4.2](#)) will be fixed across a set of values specified in the ADR ranging from very low (full borrowing) to very high (no borrowing). Summaries of the estimated treatment effect within each sensitivity analysis will be provided to assess the robustness of the primary analysis results to the degree of borrowing.

### **9.4.3. Secondary Endpoint(s)**

The following endpoints will be compared by treatment group over the treatment period:

#### **9.4.3.1. Key Secondary Endpoints**

- Proportion of participants who achieve  $\geq 50\%$  reduction from baseline in EMAS-associated seizures
- CGIC score.
- Change in total seizure frequency compared to baseline
- Change in EMAS-associated seizure frequency compared to baseline (Part B only)

